**Protocol Version Date: 17 November 2021**

## SCHEMA

### Study Timeline Schema:

### Phase 1b Schema:

**Table 1. Phase 1b Dose De-escalation Schedule**

Number of patients with DLT at a given dose level	Decision Rule
0 out of 3	Enter 3 patients at the next higher dose level
1 out of 3	Enter up to 3 additional patients at the same dose level. 
 
• If 0 of these 3 patients experience DLT, proceed to the next dose level.
 
• If 1 or more of these 3 patients experience DLT, then dose escalation is stopped and this dose is declared the maximally administered dose. Three (3) additional patients will be entered at the next lowest dose level if only 3 patients were treated previously at that dose.
 

$\geq 2$ out of 3	Dose escalation will be stopped. This dose level will be declared the maximally administered dose. Three (3) additional patients will be entered at the next lowest dose level if only 3 patients were treated previously at that dose.

[figure not shown]

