**Ascorbate Dose Levels:**

Dose 0 = Ascorbate 75 gm IV three times weekly concurrently with radiation

Dose -1 = Ascorbate 62.5 gm IV three times weekly concurrently with radiation

- Initial dose for all = Ascorbate 75gm IV

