### 5.2 Phase Ib

The phase Ib portion of this study is to ensure the safety and tolerability of high dose ascorbate in combination with EBRT as assessed by incidence of dose-limiting toxicities (DLT). Although this combination has been shown to be safe and well tolerated in GBM, this combination has not been studied in sarcoma patients. EBRT will be given at the standard dose for resectable soft tissue sarcomas according to the NCCN sarcoma guidelines. Patients will receive 50 Gy over 25 fractions for extremity and trunk sarcomas or 45 – 50.4 Gy in 28 fractions for retroperitoneal sarcomas, during which time they will be receiving three times a week IV high dose ascorbate. IV ascorbate infusions will be continued until the end of radiation therapy. Surgery will be performed 4-6 weeks from the end of radiation to allow for adequate tissue healing and resolution of acute toxicities.

Ascorbate will be dosed at an initial dose of 75gm IV three times a week concurrently with radiation therapy provided patient tolerated the test dose of ascorbate during screening without any reactions. Initially 3 patients will be entered at the Dose 0 for ascorbate and be monitored at this three times a week dose until surgery when safety issues will be addressed. Otherwise, ascorbate dose will be deescalated and dose -1 will be explored as outlined. For this protocol DLT will be defined as an attributed adverse event (definite, probable or possible) that meets the criteria (Section 6.3).

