**Table 1. Phase 1b Dose De-escalation Schedule**

Number of Patients with DLT at a Given Ascorbate Dose	Decision Rule
$\geq 2$	Dose level will be declared toxic. If this is the lowest dose level, stop the study due to excessive toxicity; otherwise enter three additional patients at the next lowest dose level.
$\leq 1$ out of 3	Enter three more patients at this dose level.
$\leq 1$ out of 6	This is the recommended dose for the subsequent Phase2.

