**Table 1. Phase 1b Dose De-escalation Schedule**

Number of Patients with DLT at a Given Ascorbate Dose	Decision Rule
$\geq 2$	Dose level will be declared toxic. If this is the lowest dose level, stop the study due to excessive toxicity; otherwise enter three additional patients at the next lowest dose level.
$\leq 1$ out of 3	Enter three more patients at this dose level.
$\leq 1$ out of 6	This is the recommended dose for the subsequent Phase2.

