## 12. STATISTICAL CONSIDERATIONS

### 12.1 Phase Ib

The primary objective of the Phase Ib portion of this study is to confirm the current standard dose of intravenous ascorbate, 75 gm, utilized in patients diagnosed with pancreatic cancer also receiving concurrent chemo radiation is safe within this population of sarcoma patients being treated concurrently with pre-operative radiation. Up to six (6) patients will be recruited to the standard dose, 75 grams administered intravenously 3 times a week during radiation therapy (5 weeks). If at most 1 out of 6 patients experience a DLT, the standard dose will be considered safe. If 2 or more patients experience a DLT, the next cohort of patients will be assigned to dose level - 1. The recommended phase II dose (RP2D) will be defined as the highest dose level for which at most 1 out of 6 patients experience a DLT.

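### The schema's Phase 1b dose table prints an escalation rule that the two listed doses cannot support and that contradicts sections 5.2, 6.2 and 12.1; section 5.3 also names Dose 0 for Phase 2 where 12.1 and 12.3 require the RP2D

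*Combined protocol and SAP*

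**What the plan says.** **Schema, Table 1.** After 0 of 3 patients with a DLT: "Enter 3 patients at the next higher dose level". After 1 of 3, up to three more are treated at the same dose, and then: "If 0 of these 3 patients experience DLT, proceed to the next dose level". When a dose fails, three further patients go to the level below, but only "if only 3 patients were treated previously at that dose". The table has no criterion for naming a Phase 2 dose and no instruction for a failure at the lowest level.

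**Schema, Ascorbate Dose Levels.** There are two levels, 75 gm (Dose 0) and 62.5 gm (Dose -1), with "Initial dose for all = Ascorbate 75gm IV".

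**Sections 5.2 and 6.2.** If Dose 0 is not tolerated, 5.2 says "ascorbate dose will be deescalated and dose -1 will be explored as outlined". Both sections print the same table:
- 2 or more DLTs: the level is toxic, and "If this is the lowest dose level, stop the study due to excessive toxicity"; otherwise three patients are entered at the level below.
- At most 1 of 3: three more at the same dose.
- At most 1 of 6: "This is the recommended dose for the subsequent Phase2".

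**Section 12.1** agrees. At most 1 of 6 means Dose 0 is safe; with 2 or more, "the next cohort of patients will be assigned to dose level - 1". The RP2D is the highest level with at most 1 DLT in 6.

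**Section 12.3** gives a Phase I size of 6 evaluable patients (minimum 6, maximum 12) and 25 patients in total treated at the RP2D.

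**Section 5.3** states the Phase 2 dose as Dose 0. Sections 5.6.1 and 5.6.3 likewise state 75 gm without qualification.

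**The concern.** DLT incidence is the Phase 1b primary endpoint, and the decision based on it sets the Phase 2 dose. The protocol prints two different rules for that decision under the same table number and title, with nothing to say which governs. Section 6.3 then refers to Table 1 for dose reduction without saying which one.

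The schema version is an ordinary escalation 3+3. Starting from the top dose, its favourable outcomes lead to a level that is not defined. Its unfavourable outcomes carry a condition that cannot be met, because no cohort has been treated at Dose -1 when Dose 0 fails. It also differs in substance from the body: at 0 of 3 it leaves Dose 0 after three patients, whereas 5.2, 6.2 and 12.1 need six before a dose can be recommended.

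The 5.3 wording matters in one scenario. If Dose 0 is declared toxic and Dose -1 becomes the RP2D, 5.3 read literally still assigns Phase 2 patients to the rejected dose.

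**Working it through.** **1. Does the body rule reproduce the plan's own Phase 1b size?** Apply the 5.2/6.2 table in cohorts of three. A level uses 3 patients if the first cohort has 2 or more DLTs, and otherwise 6.
- Dose 0 passes: 6 patients, RP2D = Dose 0.
- Dose 0 toxic after 3 or 6, Dose -1 passes with 6: 9 or 12 patients, RP2D = Dose -1.
- Both toxic: 3+3, 3+6, 6+3 or 6+6, so 6, 9 or 12 patients, and the study stops.

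The possible totals are 6, 9 and 12, which matches the minimum of 6 and maximum of 12 in 12.3. The body rule is the one the design was sized on.

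**2. Can the schema rule be followed from Dose 0?**

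| Outcome at Dose 0 | Schema instruction | Can it be carried out? |
|---|---|---|
| 0/3 | go up a level | No: nothing above 75 gm |
| 1/3, then 0/3 | go to the next level | No: same reason |
| 1/3, then 1 or more of 3 | three more one level down, if three already treated there | No: no cohort treated at Dose -1 |
| 2 or more of 3 | as above | No: as above |

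**3. How often would each problem be met?** The documents state no DLT rate for this regimen, so p = 5, 10, 20 and 30% are assumptions. Write q = 1 - p.

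Schema points to a level that does not exist: A = q³ + 3pq² × q³.
- 5%: 0.857 + 0.116 = 0.973
- 10%: 0.729 + 0.177 = 0.906
- 20%: 0.512 + 0.197 = 0.709
- 30%: 0.343 + 0.151 = 0.494

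Dose 0 declared toxic under 5.2/12.1: F = 1 - q⁶ - 6pq⁵. Stopping early at 2 DLTs in the first three does not change this.
- 5, 10, 20, 30%: 0.033, 0.114, 0.345, 0.580 (0.3446 before rounding at 20%, so 34%)

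Section 5.3 conflicts with the RP2D only if Dose 0 fails **and** Dose -1 passes; if both fail, the study stops and there is no RP2D. With the same rate at both doses: C = F × (1 - F).
- 5%: 0.033 × 0.967 = 0.032
- 10%: 0.114 × 0.886 = 0.101
- 20%: 0.345 × 0.655 = 0.226
- 30%: 0.580 × 0.420 = 0.244

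If Dose -1 is safer than Dose 0, the probability lies between C and F. F is the ceiling, reached if Dose -1 always passes.

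| Assumed DLT rate | 5% | 10% | 20% | 30% |
|---|---|---|---|---|
| Schema instruction names no existing level | 97% | 91% | 71% | 49% |
| 5.3 conflicts with RP2D, equal rates | 3% | 10% | 23% | 24% |
| 5.3 conflict, ceiling | 3% | 11% | 34% | 58% |

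**4. Is the Phase 2 test affected?** Section 12.2 uses 25 patients and success at 6 or more. The exact binomial gives P(X ≥ 6) = 0.033 at a 10% response rate and 0.807 at 30%, against the stated 0.03 and 81%. Neither depends on the wording at issue.

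**The case against.** The strongest reply is that this is a drafting slip in a summary table. The working rule is printed twice in identical form, restated in 12.1, and consistent with 12.3. The schema table's own title says de-escalation, only a lower level is listed, and both rules move downward when Dose 0 fails. A careful reader would recover the intended rule. All of that stands, and it limits the weight of the point. It does not remove the contradiction, because neither table is marked as governing.

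A similar defence covers 5.3: since 12.1 and 12.3 require the RP2D, the mention of Dose 0 may be loose wording. That is a fair reading of 5.6.1 and 5.6.3, because 5.6.6 refers to dose modifications and the infusion table has a 62.5 g row. Section 5.3 is the section that describes Phase 2 treatment, so the wrong dose there is worth correcting even if the intent is clear.

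It is tempting to treat only the low DLT rates as realistic. Section 1.3 reports no DLTs in 9 patients, but with gemcitabine rather than radiation. With 0 of 9, the exact 95% upper bound is 1 - 0.05^(1/9) = 28% one-sided and 1 - 0.025^(1/9) = 34% two-sided. Section 5.2 also says the combination is untested in sarcoma. Rates of 20 to 30% cannot be ruled out, so the full range is shown.

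**Conclusion.** The point holds as an internal contradiction in the dose-decision rule. The schema table is wrong as written and cannot be executed with the two listed doses; the rule in 5.2, 6.2 and 12.1 is coherent and reproduces 12.3. Section 5.3 disagrees with 12.1 and 12.3 in one contingency, with a probability of about 3 to 24% over assumed DLT rates of 5 to 30% if the doses share the rate, and at most 3 to 58%.

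Three stronger readings are not supported:
- **That patients might be escalated above 75 gm.** No such level is defined, so no such dose can result.
- **That 97 or 91% measures harm.** It is how often someone using the schema table alone would meet an instruction that cannot be carried out. The body supplies the correct action.
- **That the design or its error rates are compromised.** The sample size of 25, the threshold of 6, alpha of 0.033 and power of 0.81 are unchanged. If Dose 0 passes, 5.3 and 12.3 agree.

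The plan should be corrected because the rule decides the Phase 1b primary endpoint and the Phase 2 dose, and because 5.3 taken literally would name a dose already declared toxic.

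**What to change.** - Replace the Schema's Phase 1b table with the table printed in 5.2 and 6.2.
- In 5.3, name the RP2D in place of Dose 0 as the Phase 2 dose.
- As a tidy-up, replace the fixed 75 gm in 5.6.1 and 5.6.3 with the assigned dose level in Phase 1b and the RP2D in Phase 2.

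This is a wording amendment. It needs no additional patients or procedures and makes no change to the statistical design.

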**Ascorbate Dose Levels:**

Dose 0 = Ascorbate 75 gm IV three times weekly concurrently with radiation

Dose -1 = Ascorbate 62.5 gm IV three times weekly concurrently with radiation

- Initial dose for all = Ascorbate 75gm IV

## 1. BACKGROUND

### 1.1 Disease Background

Adult soft tissue sarcomas (STS) constitute a wide heterogeneous group of very rare tumors, both in terms of histology and biological and clinical behavior. In contrast to major advances in the biological understanding of these heterogeneous subtypes, forward progress in the systemic treatment of sarcoma has been painstakingly slow. The prognosis of patients with metastatic or recurrent disease is poor and most of them will die from tumor progression. Taking into account differences in histology subtype, anatomic location of disease and age at disease onset, the overall median survival for patients with metastatic STS is approximately one year and only about 10% of these patients are alive at five years.

Control of localized disease is, therefore, of prime importance as evidenced by the National Comprehensive Cancer Network's (NCCN) current treatment guidelines. Pisters et al demonstrated that histologic grade, depth of location, and positive surgical margins are key determinants of STS recurrence. However, patients typically present late with local tumor extensions into critical adjacent structures, making complete surgical resection with uninvolved margins difficult. Preoperative radiotherapy has been shown to significantly improve local disease control, functional outcomes and survival in patients with locally advanced STS.

### 1.2 Ascorbate as an anti-tumor agent

Ascorbate (ascorbic acid, vitamin C, AsCH) is one of the early unorthodox therapies for cancer, based on two unsupported hypotheses. McCormick postulated that ascorbate protects against cancer by increasing collagen synthesis, while Cameron hypothesized that ascorbate could have anti-cancer action by inhibiting hyaluronidase and thereby prevent cancer spread. These hypotheses were subsequently promoted by Cameron and Pauling. Cameron and Campbell initially published case reports of 50 patients; some seemed to have benefited from high dose ascorbate. Cameron and Pauling then published results of 100 patients with terminal cancer that were given intravenous ascorbate. The ascorbate-treated patients were compared to 1000 retrospective controls with similar disease. Patients who received ascorbate survived on average 300 days longer than controls. A prospective study was then conducted that randomized patients to ascorbate treatment or palliative therapy. Treated patients had a median survival of 343 days vs. 180 days for controls. Smaller studies have also reported benefits of ascorbate.

[figure not shown]
To test “definitively” whether ascorbate was effective, Moertel conducted two randomized placebo-controlled studies randomized to oral ascorbate; neither study showed benefit. Subsequently, ascorbate therapy was considered ineffective. However, it was not recognized until approximately 15 years later that oral and intravenous ascorbate have strikingly different pharmacokinetics. This difference in the administration route is key. Cameron gave patients ascorbate intravenously as well as orally, while Moertel's patients received only oral ascorbate. Thus, the issue of ascorbate in cancer treatment needed to be re-examined.

The evidence for use of ascorbate in cancer treatment falls into two categories: clinical data on dose concentration relationships and laboratory data describing potential cell toxicity with high concentrations of ascorbate *in vitro*. Clinical data show that when ascorbate is given orally, fasting plasma concentrations are tightly controlled at < 100  $\mu$ M. As doses exceed 200 mg, absorption decreases, urine excretion increases and ascorbate bioavailability is reduced. In contrast, when 1.25 grams of ascorbate are administered intravenously, concentrations as high as 1 mM are

[figure not shown]
achieved. Some clinicians have infused more than 10 grams of ascorbate in cancer patients and achieved plasma concentrations of 1 to 5 mM. Thus, it is clear that intravenous administration of ascorbate can yield very high plasma levels, while oral treatment does not.

Pharmacologic ascorbate concentrations have been shown to selectively kill many cancer cell types. Chen *et al.* measured cell death in 10 cancer and 4 normal cell types using 1-hour exposures to pharmacological ascorbate. Normal cells were unaffected by 20 mM ascorbate whereas 5 cancer cell lines had EC50 values of < 4 mM, a concentration achievable by intravenous administration. In addition, cell death was independent of metal chelators, but dependent on formation of H2O2. H2O2 generation was dependent on ascorbate concentration, incubation time; [H2O2] displayed a linear increase with [AscH] and it increased as a quadratic function of ascorbate radical, ascorbate being an electron donor to O2 to form superoxide and, eventually, H2O2.

When ascorbate is infused intravenously the resulting pharmacologic concentration will distribute rapidly into the extracellular water space. *In vivo*, Chen and colleagues demonstrated that intravenous injection of ascorbate (0.25-0.5 mg/g body weight) increased baseline concentrations of ascorbate in the blood and extracellular fluid to > 8 mM as well as increased formation of H2O2. More recent studies have demonstrated that intraperitoneal doses of 4 g/kg ascorbate resulted in blood concentrations of 40 mM; tumor extracellular fluid increased to peaks of 20 mM for up to 3 hours. Our data demonstrate that pharmacologic doses of ascorbate are cytotoxic to sarcoma cell lines and that it enhances radiation therapy sensitivity *in vitro* (**Figure 1**). Additionally, we also showed that intraperitoneal administration of high dose ascorbate in combination with radiation inhibits orthotopic sarcoma growth and decreases tumor size in mice without causing an associated toxicity *in vivo* (**Figure 2**). Combined, these studies provide a foundation for pursuing pharmacologic ascorbate as a prooxidant agent in cancer therapy and specifically in sarcoma.

**Figure 1** Demonstrates that sarcoma cell lines, fibrosarcoma (HT1080) and synovial sarcoma (SW-872), are sensitive to increasing doses of pharmacological ascorbate. Cells were treated with increasing doses of ascorbate for 1 hour followed by clonogenic cell survival analysis.

**Figure 2** Pharmacological ascorbate selectively sensitizes fibrosarcoma tumors to radiation in an orthotopic murine xenograft model. An orthotopic fibrosarcoma model was utilized by injecting  $1 \times 10^6$  HT-1080 cells into the dermis of the right rear flank of athymic nude female mice. Once tumors were established, therapy was initiated with daily ascorbate (4 g kg or sodium chloride control; IP) in combination with 12 Gy IR in 2 fractions (days 2 and 4) (A) Tumor volume measurements (points +/- error) fitted with a logistical regression (line) for mice treated with daily ascorbate in combination with radiation (B) Overall survival in mice treated with ascorbate in combination with radiation. Mice were sacrificed when any tumor dimension reached 1.5 cm. NED=no evidence of macroscopic disease at end of experiment. (C) Mouse weight in mice treated with ascorbate in combination with radiation. For each treatment group, n = 8 mice.

Ascorbate-mediated cell death has been shown to be due to H2O2 generation, *via* ascorbate radical formation, with ascorbate as the electron donor. When ascorbate is infused intravenously the resulting pharmacologic concentration distributes rapidly in the extracellular water space. Thus, pharmacologic ascorbate concentrations in media, as a surrogate for extracellular fluid, should generate ascorbate radical and H2O2. In contrast, the same pharmacologic ascorbate concentrations in whole blood generate little detectable ascorbate radical and no detectable H2O2. This can be accounted for by efficient and redundant H2O2 catabolic pathways in whole blood relative to those in media or extracellular fluid. Thus, ascorbic acid administered intravenously in pharmacologic concentrations may serve as a pro-drug for H2O2 delivery to the extracellular milieu, but without H2O2 accumulation in blood.

### 1.3 Clinical Trial Data

In a Phase I trial of intravenous ascorbic acid in patients with advanced malignancy the high-dose intravenous ascorbic acid was well tolerated when administered to patients. Adverse events and toxicity were minimal at all dose levels. Ascorbic acid concentrations reached up to 25 mmol/L in patients who received ascorbic acid of 1.5 g/kg. Of the 24 patients in the study, only 4 recorded minor adverse events including headache, dizziness and diarrhea. In another phase I trial using pharmacological ascorbate concurrently with gemcitabine in patients with locally advanced and

metastatic pancreatic cancer conducted at University of Iowa Hospitals and Clinics, 9 patients received treatment. Individual doses between 50 to 125 g per infusion were given for maintenance of 350 mg/dL level in plasma. 75-g dose yielded peak plasma levels ranging between 320 and 630 mg/dL. No dose limiting toxicities or serious adverse events were reported.

A phase I study of adding ascorbate to standard therapy in glioblastomas and NSCLC was initiated in 2013. Subjects were assigned to high-dose ascorbate dose cohorts for the concomitant portion of therapy. Dose cohorts ranged from 15g to 87.5g. During the adjuvant phase, subjects underwent interpatient dose escalation to achieve a targeted plasma ascorbate level of 350 mg/dL. Subjects received high-dose ascorbate during the adjuvant phase for up to 6 cycles. To date, 5 subjects have been enrolled in the recommended phase 2 dose of 87.5g. Treatment was well-tolerated with minimal adverse events. No subject experienced a grade 3 or greater hematologic or non-hematologic toxicity. The only adverse events associated with ascorbate were grade 1 dry mouth, grade 1 chills, and grade 2 hypertension. Dry mouth is transient and ends shortly after infusion. Grade 1 chills are infusion related, most likely due to the volume of fluid infused. Grade 2 hypertension occurs in some subjects during infusion, again most likely due to the volume of fluid infused.

#### **1.4 Radiation Therapy in Sarcoma**

The benefits of combination therapy with radiation and surgery in significantly improving local control in STS patients are well documented. Preoperative radiotherapy has been shown to significantly improve local disease control, functional outcomes and survival in patients with locally advanced STS. Recent review of literature indicates that about 10% of patients will have  $\geq 95\%$  tumor necrosis, and about 25% will achieve  $\geq 80\%$  tumor necrosis following preoperative radiation therapy alone. Further review indicates that only those patients who achieve  $\geq 95\%$  tumor necrosis with preoperative radiation have improved local and distant control as well as overall survival. Despite its reported benefits, radiotherapy is associated with a high rate of complications and significant functional morbidity. O'Sullivan et al compared preoperative versus postoperative external beam radiation (EBRT) for resectable extremity STS. Long term follow up revealed no statistical difference in local control and cause specific survival, however, preoperative radiotherapy was associated with a significantly higher rate of acute wound complications (35% vs. 17%,  $p = 0.01$ ) and a lower rate of late Grade 2– 4 fibrosis (32% vs. 48%,  $p = 0.07$ ). Multiple retrospective reviews have similarly found high rates of acute wound complications in sarcoma patients ranging from 25% to 44%. These reported high rates of acute and late toxicities support the need for additional research to improve the safety profile of neoadjuvant radiotherapy.

In addition, there is need to improve efficacy of the radiation treatments to achieve higher rates of tumor necrosis, and, to ensure resection of the tumor with clear margins for successful organ preserving treatment of sarcoma.

